8.8 Adverse Events Related To r-tPA And Definition Of Major Bleeding

AEs related to r-tPA are well-described and consist mainly of bleeding complications, including intracranial hemorrhage. The incidence of these complications has been quantified in subjects receiving comparatively large systemic doses of r-tPA for acute myocardial infarction, stroke, and acute PE. Any bleeding that is attributable to r-tPA is most likely to occur within 24 hours of treatment and is very unlikely to occur after 72 hours. Therefore, all bleeding events without known cause that occur within 72 hours of the APT Procedure will be attributed to the use of r-tPA.

The following definition of major bleeding¹² (ISTH) will be used: As general principles, a definition of major bleeding will be based on objective criteria, and major bleeds are those that result in death, are life-threatening, cause chronic sequelae or consume major health-care resources. With this in mind, the Control of Anticoagulation Subcommittee recommends the following criteria for major bleeding in non-surgical subjects:

1. Fatal bleeding, and/or
2. Symptomatic bleeding in a critical area or organ, such as intracranial, intraspinal, intraocular, retroperitoneal, intra-articular or pericardial, or intramuscular with compartment syndrome, and/or
3. Bleeding causing a fall in hemoglobin level of 20 gL^{-1} (1.24 mmol L^{-1}) or more, or leading to transfusion of two or more units of whole blood or red cells

For this protocol, a fall in Hgb of 20 gL^{-1} or more with no objective evidence of bleeding or symptoms of bleeding will not be considered a major bleeding event.

8.9 Specific Reporting Guidelines

Study Investigators will adhere to the following guidelines to ensure the quality and precision of AE reporting:

1. Use recognized medical terms.
2. Avoid the use of colloquialisms and non-standard abbreviations
3. If known at the time of AE reporting, a diagnosis will be reported instead of individual symptoms and signs (for example, record only “pneumonia” rather than “productive cough” and “elevated white blood cell count”).
4. If the reported symptoms and signs cannot be medically characterized as a single diagnosis or syndrome at the time of AE reporting, the information that is available will be reported. If a diagnosis is subsequently established, it will be reported as follow-up information as described earlier.
5. A cascade of clinical events (such as sequelae of an adverse event) will be identified as the primary, causative event.

6. Any AE potentially related to the study procedure that results in inpatient re-hospitalization or prolongs the index hospitalization will be reported as a SAE. If a subject is re-hospitalized to undergo a medical or surgical procedure as a result of an AE, the event responsible for the procedure (not the procedure itself) will be reported as the SAE. For example, if a subject is re-hospitalized to undergo exploratory surgery as a result of a major bleeding event, record the major bleeding event that necessitated surgery as the SAE.
7. All observed or reported serious bleeding events occurring through the 365 day follow-up period, must be recorded.
8. Previously scheduled hospitalizations required for diagnostic or elective surgical procedures for the management of unchanged pre-existing medical conditions will not be considered AEs.

8.10 Pregnancy

If a subject becomes pregnant within 90 days of receiving r-tPA and undergoing APT Procedure, follow-up will be obtained from the medical record to determine the outcome of the pregnancy (successful live-birth, etc.). Congenital abnormalities must be reported as a SAE.

8.11 Categorization Of Adverse Events

All AEs must be classified according to intensity or severity, relatedness, outcome, and treatment or action taken.

Intensity Or Severity

The following categories for intensity or severity of an AE will be used in reporting:

Mild	Awareness of a symptom or sign that does not interfere with the subject's usual activity or is transient and resolves without treatment and without sequelae
Moderate	Interferes with the subject's usual daily activities, but he or she is still able to function
Severe	Interrupts a subject's usual daily activities and generally requires medication, surgery, or other intervention for treatment

Relatedness

Each AE will be evaluated as to whether it was related to the study procedures, thrombolytic and anticoagulation drugs, or EKOS as follows:

Definite	An AE that has a causal relationship to the drug (r-tPA), anticoagulation medication, or EKOS
Probable	An AE that has a 'reasonable possibility' of a causal relationship to the use of r-tPA, anticoagulation medication, or EKOS; another etiology is significantly less likely
Not related	An AE is not related to the use of r-tPA, anticoagulation medication, or the APT® Endovascular System; there is no temporal relationship or a much more likely alternative etiology exists
Unknown	An AE where the relationship to the use of r-tPA, anticoagulation medication, or EKOS cannot be determined.

Outcome

The clinical course of all AEs will be followed until a medical outcome is determined (resolution, stabilization, or determination that it was unrelated to study participation). The clinical outcome of all AEs will be recorded as follows:

Death	Subject expired
Recovered	Subject returned to baseline health and functional status

Not yet recovered	Subject did not recover and symptoms or sequelae persist
Recovered with sequelae	Subject did recover but continues to experience clinical sequelae from the adverse event

Treatment or action taken

AEs and SAEs will be categorized by the actions taken in response to the event:

Intervention	Surgery or other invasive procedure
Non-surgical treatment	Drug start, interruption, dose reduction, dose increase, or discontinuation
None	No action was taken

8.12 Expedited Reporting Of Serious Adverse Events

Any AE that is considered serious must be reported to the device manufacturer, EKOS Corporation, within 24 hours of the site's knowledge of the event throughout the study. The Investigator will enter into EDC as much of the information listed below is available within 24 hours. An automatically generated email notification will be sent to EKOS when the event is classified as a Serious Adverse Event in EDC.

- a. Subjects demographics
- b. Pre-existing conditions
- c. The adverse event's description
- d. Date and time of AE onset
- e. Severity
- f. Treatment
- g. Results of diagnostic testing
- h. Duration of sequelae
- i. Outcome (if known)
- j. Information on suspected medications

When a device-related SAE is reported, the device must be retained and returned to EKOS (see above for address for return devices). The EKOS representative may contact the Investigator to collect additional information on EKOS.

When reporting a death, the primary event or condition that caused or contributed to the fatal outcome will be reported as the serious adverse event. Death would be reported as the outcome of the serious adverse event. If the cause of death is unknown at the time of reporting, record “unknown cause of death.”

8.13 Safety Monitor

A safety monitor will review all AEs, adjudicate all SAEs and major bleeding events during the study, as well as assess freedom from major harm occurring between enrolment and 30 days for each subject. The safety monitor will determine if the AE meets the definition of serious and unexpected and will notify EKOS if the number or type of events is of concern.

9 DATA COLLECTION

All study data will be recorded in eCRFs. Images will be provided to the Core Imaging Laboratory as described in the operations manual provided to the sites. Instructions and training on data collection/entry will be provided to the Investigator and their staff during site start-up and will be available throughout the study for new personnel.

Data gathered during the course of the study will be entered into an eCRF as soon as possible and at least within 7 days of subject enrollment or follow-up visit. Data will be reviewed on a periodic basis and any incomplete or inconsistent data will be requested from the Investigator.

10 STATISTICAL ANALYSIS

10.1 Analysis Subject Sets, Evaluable Subjects and Missing Data Handling Convention

Intent-to-Treat (ITT) Subject Set includes all randomized subjects; analyses performed on the ITT Subject Set will be by randomization treatment assignment regardless of actual treatment’s deviations from the assigned treatment protocol. Unless otherwise specified, all available data will be used for ITT analyses regardless of whether the assessment timing is within the pre-specified window.

Efficacy Evaluable Subject Set are defined as randomized subjects who met all eligibility criteria, received the randomization assigned APT Procedure with bilateral EkoSonic treatment, and for whom CTA imaging data are available and the assessments are within the pre-specified window at both Screening/Baseline (within 48 hours prior to APT start) and 48 ± 6 hours from the beginning of the APT procedure.

Safety Evaluable Subject Set are defined as randomized subjects for whom the APT Procedure was initiated, i.e. venous access attempted for EkoSonic catheter introduction. Safety analysis will be performed on the Safety Evaluable Subject Set according to the actual treatment received.

Missing data will not be imputed for the efficacy and safety analyses.

10.2 General Methodology

Unless otherwise specified, all analysis will be performed separately for each of the treatment arms and separately for unilateral and bilateral patients within each treatment arm. For Screening/Baseline demographics and subject or disease characteristics, continuous measures will be summarized as mean, standard deviation, median, minimum and maximum. Categorical data will be summarized as frequencies and percentages for each data category. For changes from Screening/Baseline to follow-up time points, continuous measures will be summarized as mean, standard deviation, median, minimum, and maximum. Categorical outcomes will be summarized in two-way tables. Statistical significance for changes from Screening/Baseline will be assessed by t-test or a nonparametric test as appropriate for continuous data; Fisher's exact test will be done for 2x2 tables and Friedman Halton exact test will be performed for tables with higher dimensions.

Further analysis details will be described in the Statistical Analysis Plan.

10.3 Efficacy Analyses

Efficacy analyses will be performed on both the **ITT Subject Set** and the **Efficacy Evaluable Subject Set**.

10.3.1 Primary Efficacy Analysis

The primary efficacy outcome is the change in the RV diameter-to-LV diameter ratio, from Screening/Baseline to 48 hours after the start of the APT Procedure, as determined by CTA. For each treatment arm, the mean RV/LV ratio change will be compared to the historical control value of a 0.20 reduction for the heparin arm²⁸. For this study, a 1-sided $p < 0.15$ rejecting a ≤ 0.20 reduction will be regarded as a positive sign for further investigating a treatment regimen. As an example, should the standard deviation be 0.41 as observed in the SEATTLE II study, with 25 evaluable subjects the 1-sided p value would be <0.15 if the mean RV/LV ratio reduction is 0.29 or higher. To limit the 3-arm total false positive error rate to 0.15, the Hochberg procedure²⁹ will be used for statistical testing.

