10.5 Sample Size And Power Estimation

The primary efficacy endpoint for the study is the 48-hour decrease in RV/LV ratio. The Fasullo study's heparin arm indicated a mean RV/LV ratio decrease of 0.20. Based on these results, we propose a mean 48-hour RV/LV ratio (absolute) decrease ≤ 0.20 as the null hypothesis for this study. Rejecting the null hypothesis with a 1-sided $p<0.15$ by t test will be regarded as a positive sign for further investigating a treatment regimen. For sub-massive PE subjects in the SEATTLE II study, a mean RV/LV ratio reduction of 0.43 was observed with a standard deviation of 0.41. Should these results be true for a regimen in the current study, with 25 evaluable subjects, the power to detect a positive signal is approximately 0.95.

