Enrollment:	
OPTALYSE PE 101 subjects were randomized and 100 treated in the OPTALYSE PE study and were followed for one year.
 
OPTALYSE PE – UK Extension (OPTALYSE UK) Up to 120 additional subjects were planned to be enrolled in the UK Extension study to obtain up to 75 efficacy evaluable subjects (25 efficacy evaluable subjects enrolled and randomized in each of 3 treatment arms.). Due to slow enrollment and the ability for sites to participate in the KNOCKOUT study, the OPTALYSE UK sites were instructed to stop enrollment on May 1, 2019. 29 subjects were enrolled in OPTALYSE UK and sites were instructed to continue following subjects for one 1 year per the protocol.
 
Evaluable subjects are those who have RV/LV assessments within specified windows and scores available at baseline and at 48 hours from the start of treatment.
																			

A. PROTOCOL SYNOPSIS

Clinical Sites:	
OPTALYSE PE 19 centers within the United States and the United Kingdom enrolled into OPTALYSE PE.
 
OPTALYSE PE – UK Extension (OPTALYSE UK) Up to 10 centers located in the United Kingdom were planned for OPTALYSE UK. At the time enrollment was stopped, 5 sites had enrolled subjects into OPTALYSE UK.

Time Course:	
OPTALYSE PE Enrollment into OPTALYSE PE took place from June 2015 through November 2016 with 1 year follow-up.
 
OPTALYSE PE – UK Extension (OPTALYSE UK) Enrollment into OPTALYSE UK took place from October 2017 through March 2019 with 1 year follow-up.

B. SCHEDULE OF ASSESSMENTS - OPTALYSE UK

	Screening/ Baseline ¹	Post APT Procedure				Follow-up - Clinic Visit			
	Day -2 within -48 Hrs. of APT start	Day 0 within 4 Hrs. of APT end	Day 1 24 Hrs. ±6 hrs of APT start	Day 2 48 Hrs. ±6 hrs of APT start	Day 3 72 Hrs. of APT start or D/C ¹⁰	Day 30 ± 5 D	Day 90 ± 10 D	Day 365 ± 14D	Early Term ¹¹
Informed Consent	X								
Demographics	X								
Medical History, Physical Exam, & Risk Factors	X								
Vital Signs ^{2,3}	X	X	X	X		X	X	X	X
Electrocardiogram	X								
CTA	X			X					
Hemodynamics/SvO ₂ ⁴	Optional								
PESI/sPESI	X	X	X	X					
Echocardiogram ^{5,6}	X	X	X	X		X	X	X	X
Laboratory Tests ⁷	X	X		X					
Biomarkers: Troponin, BNP/NT-proBNP, lactate/lactic acid, and D-dimer	X			X					
6 Minute Walk Test (6MW)						X	X	X	X
QOL Assessment: PEmb-QOL; EQ-5D- 5L						X	X	X	X
Adverse/VTE/Bleeding Events		X	X	X	X	X	X	X	X
Anticoagulant medications ⁸	X	X	X	X	X	X	X	X	X
Concomitant medications ⁹	X	X	X	X	X	X	X	X	X

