2.3 Efficacy Analyses

2.3.1 Primary Efficacy Analysis

The primary efficacy outcome is the change in the RV diameter-to-LV diameter ratio, from Screening/Baseline to 48 ± 6 hours after the start of the APT procedure, as determined by CTA. For each treatment arm, the mean RV/LV ratio change will be compared to the historical control value of a 0.20 reduction for the heparin arm¹. For this study, a 1-sided $p < 0.15$ by t test rejecting a ≤ 0.20 reduction will be regarded as a positive sign for further investigating a treatment regimen. As an example, should the standard deviation be 0.41 as observed in the SEATTLE II study, with 25 evaluable subjects the 1-sided p value would be <0.15 if the mean RV/LV ratio reduction is 0.29 or higher. To limit the 3-arm total false positive error rate to 0.15, the Hochberg procedure² will be used for statistical testing.

The main primary endpoint analyses will be performed for the ITT Subject Set and the Evaluable Subjects subset.

To explore a potential increasing trend in RV/LV ratio reduction for treatment Groups 1 through 3 as defined in Protocol Synopsis, i.e. Group 1 having the least reduction and Group 3 having the most reduction, an exploratory regression analysis will be performed on both absolute change and percent change data from all 3 groups. The independent variables will include baseline RV/LV ratio value, the unilateral vs. bilateral PE indicator, and treatment groups 1 through 3 coded ordinally as 1, 2, and 3. This exploratory analysis will only be performed on the ITT Subject Set.

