2.5 Sample Size And Power Estimation

The primary efficacy endpoint for the study is the 48-hour decrease in RV/LV ratio. The Fasullo¹ study's heparin arm indicated a mean RV/LV ratio decrease of 0.20. Based on these results, we propose a mean

48-hour RV/LV ratio (absolute) decrease ≤ 0.20 as the null hypothesis for this study. Rejecting the null hypothesis with a 1-sided $p<0.15$ by t test will be regarded as a positive sign for further investigating a treatment regimen. For submassive PE subjects in the SEATTLE II study, a mean RV/LV ratio reduction of 0.43 was observed with a standard deviation of 0.41. Should these results be true for a regimen in the current study, with 25 evaluable subjects, the power to detect a positive signal is approximately 0.96.

The simultaneous power for the three treatment groups at the planned sample size of with $n=25$ evaluable per arm is approximately 0.88 by the Hochberg procedure².

Appendix 1: List of Tables (All summaries and analyses will be by treatment arm for the UK Extension portion of the study unless otherwise specified. Except for RV/LV ratio analyses, all p values are 2-sided. Analyses that will be conducted for the combined portions of the study (OPTALYSE PE plus UK Extension) as well as for the UK Extension alone and are indicated by an asterisk.)

Subject Set = ITT for (1) – (20) Unless Otherwise Specified

- 1) Enrollment by Site
- 2) Demographics
 - a) Age
 - b) Weight
 - c) BMI
 - d) Gender
 - e) Ethnicity (Hispanic vs. not Hispanic)
 - f) Race
- 3) Clinical History and Risk Factors
 - (a) – (v) on *Clinical History and Risk Factors CRF*.
 - a) Hypercholesterolemia
 - b) Congestive Heart Failure
 - c) Hepatic Insufficiency
 - d) Renal Insufficiency
 - e) TIA or Stroke
 - f) Active Cancer
 - g) Diabetes
 - h) Hypertension
 - i) Tobacco use
 - j) $BMI \geq 30.0$
 - k) COPD
 - l) History of Cancer in Remission
 - m) Family History of VTE
 - n) Chronic Inflammatory Disorders
 - o) Acute Infectious Illness within 30 Days of signing ICF
 - p) Atherosclerotic Cardiovascular Disease
 - q) Currently taking a Hormonal Contraceptive or Replacement Therapy
 - r) Osteoarthritis of Either Hip or Knee

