11) Core Lab RV/LV ratio from CTA: Baseline, 48 hours Post APT Start, absolute difference (Post-Procedure - Baseline) and percent change*

Summarize as continuous data for all above, i.e. n, mean, SD, median, minimum, maximum; provide 95% CI's for mean absolute and percent changes; provide 1-sided and 2-sided p values testing reduction ≤ 0.20 by t test for mean absolute change from baseline; provide same p values testing reduction ≤ 0 by t test for mean percent change from baseline.

All analyses above for RV/LV ratio by CTA will be repeated for the efficacy evaluable patient subset for ITT patients.

Lastly, repeat the above analyses for ITT patients as 6 arms, i.e. unilateral vs. bilateral for each of the 3 randomization arms.

Using continuous data from all 3 arms, perform increasing benefit trend analysis as described in the last paragraph of Section 2.3.1 and provide the 2-sided p value. (ITT only)

12) Core lab echocardiogram: Baseline, within 4 hours of APT end, 24 and 48 hours post APT start, Day 30, Day 90, Day 365 (procedure start date = Day 0) and change from baseline at all post-baseline time points (for continuous endpoints a-c below, besides summarizing as n, mean, SD, median, minimum and maximum at each of the 7 time points, also provide box-wisker plots for all time points on the same graph)*

- RV/LV ratio (perform same analysis at all time points as for the primary endpoint of RV/LV ratio as described in (11) above with the exceptions that testing a mean reduction of 0.20 applies to the 48 hours time point only and binary endpoint applies to \leq baseline vs. $>$ baseline only) (ITT)
- TAPSE (perform same analysis at all time points as for the primary endpoint of RV/LV ratio as described in (11) above, except mean absolute changes from baseline are tested against 0 as opposed to 0.20 and all p values are 2-sided and binary endpoint applies to \leq baseline vs. $>$ baseline only) (ITT)
- Estimated RVSP (perform same analysis at all time points as for the primary endpoint of RV/LV ratio as described in (11) above, except mean absolute changes from baseline are tested against 0 as opposed to 0.20 and all p values are 2-sided and binary endpoint applies to \leq baseline vs. $>$ baseline only) (ITT)
- IVC collapse with respiration (summarize as frequency and proportion at each time point and 2 \times 2 tables for changes from baseline, provide p values by McNemar's test) (ITT)

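### The per-arm test against 0.20 ignores baseline RV/LV: it is valid on average, but inefficient, and an arm's chance starting severity influences whether it passes

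*Protocol*

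**What the plan says.** Protocol 10.3.1 and SAP 2.3.1 set the same decision rule. For each arm, "the mean RV/LV ratio change will be compared to the historical control value of a 0.20 reduction". A one-sided p below 0.15 "rejecting a ≤ 0.20 reduction will be regarded as a positive sign for further investigating a treatment regimen", with Hochberg across the three arms. SAP Appendix 1 item 11 gives the calculation: "provide 1-sided and 2-sided p values testing reduction ≤ 0.20 by t test for mean absolute change from baseline". No covariate enters it. The same item tests percent change, but against 0, so that row does not replace the decision test.

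Baseline is used elsewhere. For the exploratory trend regression on this endpoint, SAP 2.3.1 says "The independent variables will include baseline RV/LV ratio value", among others. SAP 2.3.2 puts the baseline value into the echocardiographic repeated-measures models.

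The sample size sections assume 25 evaluable subjects per arm. The SAP synopsis (Enrollment) reports that recruitment was stopped and that "29 subjects were enrolled in OPTALYSE UK".

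**The concern.** The endpoint is baseline minus 48-hour value, so some positive correlation between reduction and baseline is to be expected. An arm that happens to receive patients with larger ratios would then tend to show a larger mean reduction whatever its regimen does, and an arm with milder patients a smaller one. The test that decides which regimens merit further study makes no allowance for this, although the baseline CTA value is collected for eligibility and the SAP treats it as relevant in other models.

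Two things are at stake. A regimen could be taken forward or dropped partly because of its baseline draw, and precision already available in the data goes unused in a small extension. Because the arms are randomised, they share one expected baseline. An arm mean adjusted to the all-arm baseline therefore estimates the same quantity as the raw mean, with less error when r is not zero.

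**Working it through.** **Inputs from the documents.** Null reduction 0.20, one-sided 0.15, Hochberg over three arms (Protocol 10.3.1). For SEATTLE II, "a mean RV/LV ratio reduction of 0.43 was observed with a standard deviation of 0.41" (Protocol 10.5). Planned n = 25 per arm; 29 enrolled in the UK extension.

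**Assumptions.** The correlation r is taken as 0, 0.3, 0.5 and 0.7. Allocation is taken as equal, 10/10/9 (29/3 = 9.7). Data are normal with a common linear slope. The simulations set the baseline SD at 0.40, but only r affects the results.

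**1. Reproduce the plan (n = 25).** SE = 0.41/√25 = 0.082. The p < 0.15 threshold is a mean reduction of 0.287, matching the plan's 0.29. Noncentrality = 0.23/0.082 = 2.80, which gives power 0.959. The Protocol says "with 25 evaluable subjects, the power to detect a positive signal is approximately 0.95" and the SAP says "with 25 evaluable subjects, the power to detect a positive signal is approximately 0.96"; both are close enough. All three arms pass under Hochberg when the largest p is below 0.15: 0.959³ = 0.88, the SAP's figure.

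**2. Effect of sample size alone.** Raw power is 0.753 at n = 10 and 0.722 at n = 9. The average over 10/10/9 is (2 × 0.753 + 0.722)/3 = 0.74, and all-three power is 0.753² × 0.722 = 0.41.

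**3. Effect of the baseline draw (n = 10).** If an arm's mean baseline is 1 SE above expectation, its expected mean reduction shifts by r × 0.41/√10: 0.039 (r = 0.3), 0.065 (0.5) or 0.091 (0.7). To pass, the arm needs about 0.343, which is 0.143 above the null.

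**4. Variance after adjustment.** Evaluate each arm at the all-arm mean baseline, with N = 3n, fitted slope b and baseline SD s_x, so that b·s_x = r × 0.41. Ignoring the small term for imbalance between arms:

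Var = 0.41²(1 − r²)/n + b²s_x²/N = (0.41²/n)(1 − r² + r²/3) = (0.41²/n)(1 − 2r²/3).

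The factor is 0.94, 0.83 and 0.67 for r = 0.3, 0.5 and 0.7.

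**5. Simulation at 10/10/9** (raw / adjusted). Per-arm columns use one-sided 0.15 before Hochberg. Repeat runs differ by about 0.01.

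| r | Per-arm power | All three pass | At least one passes | False positive, arm baseline > 1 SE high (true 0.20) | Pass rate, arm baseline > 1 SE low (true 0.43) |
|---|---|---|---|---|---|
| 0 | 0.74 / 0.74 | 0.41 / 0.41 | 0.89 / 0.89 | no dependence | no dependence |
| 0.3 | 0.74 / 0.77 | 0.41 / 0.46 | 0.89 / 0.90 | 27% / 19% | 59% / 71% |
| 0.5 | 0.74 / 0.80 | 0.41 / 0.52 | 0.89 / 0.92 | 37% / 22% | 46% / 71% |
| 0.7 | 0.74 / 0.85 | 0.41 / 0.65 | 0.89 / 0.93 | 49% / 27% | 32% / 73% |

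**6. Error control.** Averaged over baseline draws, the raw test has per-arm error of about 0.15 and Hochberg any-arm error of about 0.145 to 0.150. With a common slope, adjusted per-arm error is 0.144 to 0.154. Leaving out b²s_x²/N raises it at n = 10 to 0.162 (r = 0.5) or 0.183 (r = 0.7), so that term is needed. With strongly unequal slopes (arm correlations 0.2/0.5/0.8), adjusted per-arm error is about 0.17/0.15/0.12, while any-arm error stays below 0.15.

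**The case against.** The strongest reply is that nothing in the plan is wrong. Baseline variation is already inside the SD of 0.41, so the raw test keeps its level. It needs no model, and it serves a lenient screen rather than a confirmatory claim. Item 11 already tabulates baseline RV/LV by arm, so imbalance will be visible. The gain depends on an undocumented correlation: it is nil at r = 0. At r = 0.3 it is 2 to 3 points of per-arm power, about half of which comes from pooling the SD across arms rather than from baseline. The adjusted test also adds a common-slope assumption and a non-standard standard error.

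Most of this stands. It makes the point one of efficiency and of sensitivity to the baseline draw, not of validity. It does not remove the point. Seeing an imbalance in a table does not say what to do about it when the decision follows the raw p value, and the existing trend regression gives no arm-specific test against 0.20. The planned analysis combined with the first cohort improves power but not the dependence on the draw, because the shift and the standard error shrink together. At 25 per arm and r = 0.7, the high-baseline false-positive rates are still about 50% raw and 27% adjusted.

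A reader might infer that the unadjusted test inflates error, pointing to the 49%. That figure is conditional on a high baseline, which about 16% of arms would have, and on r = 0.7. The matching low-baseline rate is about 0.5%, and the average is 0.15.

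**Conclusion.** The decision test is valid on average but less efficient than the data allow, and an arm's chance baseline influences whether it passes. At 10/10/9 the forgone per-arm power is about 0, 3, 6 and 11 points for r = 0, 0.3, 0.5 and 0.7. All-three power would rise from 0.41 to as much as 0.65. The chance of at least one passing arm hardly changes.

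These figures assume equal allocation, a common linear slope and SEATTLE II's mean and SD. The arm sizes are an upper bound, because the synopses base the primary analysis on bilaterally treated patients and the evaluable set drops those without in-window CTAs.

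Two stronger readings are not supported. Omitting baseline does not explain the fall in power from 0.96 to 0.74; that comes from n dropping from 25 to about 10, and adjustment does not restore it. Nor would adjustment make the comparison with 0.20 fairer to the historical heparin arm. The documents do not give that arm's baseline, and centring on this trial's mean leaves any trial-wide difference in severity in place.

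**What to change.** In Protocol 10.3.1, SAP 2.3.1 and Appendix 1 item 11, name the baseline-adjusted arm mean as the tested quantity:

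- Fit one ANCOVA of RV/LV reduction on arm and baseline CTA RV/LV, evaluated at the all-arm mean baseline.
- Test each adjusted mean against 0.20, one-sided, then apply Hochberg.
- Use SE² = s²_res[1/n + (x̄_arm − x̄)²/S_xx] + b²s_x²/N on N − 4 degrees of freedom, where S_xx is the within-arm sum of squares of baseline. A bootstrap that resamples baseline is an alternative.
- Report the raw one-sample t test and baseline RV/LV by arm in the same table, with a check for differing slopes and a comment if the two tests disagree.

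This must be fixed before results are examined. The SAP is dated November 2019 and gives March 2019 as the end of enrolment, so the 48-hour scans were already complete. If outcomes by arm have been seen, label the adjusted result post hoc and keep the raw test as the decision rule.

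The cost is a wording change and one model on data already collected. The downside is the common-slope assumption, with the per-arm error drift shown above if slopes differ strongly.
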